Inclusion criteria will be: 1) age 50-70, 2) stroke within the past 6 to 24 months, 3) residual paresis in the lower extremity (Fugl-Meyer LE motor score <34), 4) ability to walk without assistance and without an AFO on the treadmill \geq 30 seconds at speeds ranging from 0.3 - 0.8 m/s, and 5) provision of informed consent. In addition, all subjects who meet criteria for the training portion must complete an exercise tolerance test and be cleared for participation by the study cardiologist. **Exclusion criteria** will be: 1) Unable to ambulate at least 150 feet prior to stroke, or experienced intermittent claudication while walking; 2) rating on Modified Ashworth Scale ≥ 3 at the knee or ankle; 3) limited lower extremity range of motion of the knee (passive flexion ROM < 90); hip (inability to achieve neutral 0° hip extension); or ankle (inability to achieve 0° of active dorsiflexion); 4) history of congestive heart failure, unstable cardiac arrhythmias, hypertrophic

cardiomyopathy, severe aortic stenosis, angina or dyspnea at rest or during ADL's; 5) History of COPD or oxygen dependence; 6) Preexisting neurological disorders, dementia or previous stroke; 7) History of major head trauma; 8) Legal blindness or severe visual impairment; 9) history of significant psychiatric illness 10) Life expectancy <1 yr., 11) Severe arthritis or other problems that limit passive ROM; 12) post-stroke depression (PHQ-9 ≥ 10), 13) History of DVT or pulmonary embolism within 6 months; 14) Uncontrolled diabetes with recent diabetic coma, or frequent insulin reactions; 15) Severe hypertension with systolic >200 mmHg and diastolic >110 mmHg at rest; 16) Previous or current enrollment in a trial to enhance motor recovery; 17) Presence of non-MR compatible implants, pregnancy or severe claustrophobia.

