without pedaling for two minutes. Exercise will begin with the subject pedaling at ~60 revolutions per minute (RPM) and 0 Watts (W) of workload. The workload will be increased by ~10 W every 3 minutes. If the subject's cadence drops below 50 RPM, additional reminders to pedal at 60 RPM will be given. Testing continues until maximal effort is achieved. Maximal effort is defined as the achievement of 90% maximal age-predicted heart rate (maximum heart rate = 220-age). The test will be terminated prior to achieving maximum heart rate for predefined symptomatic, clinical, and electrocardiographic criteria. Symptom-related reasons for termination include angina, dyspnea, and fatigue. Fatigue is defined as either voluntary exhaustion or inability to maintain a minimum cycling cadence of 40 RPM. Clinical criteria for termination include: 1) Hypertension: $\geq 220/120$ mmHg, or 2) Hypotension: a drop in diastolic blood pressure >20 mmHg, and O₂ saturation $<85\%$. Electrocardiogram criteria include: 1) ≥ 1 mm horizontal or down sloping ST segment depression, 2) sustained paroxysmal ventricular tachycardia (>30 beats), and 3) sustained paroxysmal supraventricular tachycardia (>30 beats). A 5 minute cool down period will immediately follow test termination. If the test is terminated because of electrocardiographic findings, the subject will be managed medically as needed, referred for care, and disapproved for participation. Brachial artery blood pressure from the subject's non-paretic upper extremity will be measured using an automated blood pressure monitor. Resting blood pressure and heart rate will be obtained prior to initiation of exercise as well as after the subject has been sitting on the stationary bicycle for 1 minute. During the graded exercise test, blood pressure readings will be obtained every 3 minutes. Heart rate will be obtained from the 12-lead EKG. Maximal heart rate will be recorded as the highest heart rate achieved during the exercise tolerance test.

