Subject monitoring during testing and training: Blood pressure (BP) and heart rate (HR) will be monitored prior to, during, and at completion of each session. Subjects' resting diastolic BP must be <100 mmHg, systolic < 200 mmHg, and heart rate <110 beats/min to begin the testing (Mahler et al, 1995, Rimmer et al, 2000). Criteria for termination include subject complaints of shortness of breath, light-headedness, confusion, severe headache, or dyspnea; onset of angina; excessive blood pressure (systolic BP > 200 mm Hg, diastolic BP >110 mm Hg), or drop in systolic BP >10 mm Hg and inappropriate bradycardia (drop in heart rate >15 bpm).

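### The stopping criteria for the exercise tolerance test, study testing and training sessions contradict each other or can be read two ways, and need to be reconciled

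*Combined protocol and SAP*

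**What the plan says.** Three places in the combined protocol and SAP set stopping criteria for exercise.

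- **Section D, Exercise Tolerance Testing.** "Symptom-related reasons for termination include angina, dyspnea, and fatigue". Two clinical stops are numbered. The first is hypertension at or above 220/120 mmHg. The second is "Hypotension: a drop in diastolic blood pressure >20 mmHg, and O₂ saturation" below 85%. Three ECG stops follow, each with its own number. The consequence of a stop is written for one group only: "If the test is terminated because of electrocardiographic findings, the subject will be managed medically as needed, referred for care, and disapproved for participation".
- **Section D, the monitoring section that comes next.** It opens: "Subject monitoring during testing and training: Blood pressure (BP) and heart rate (HR) will be monitored prior to, during, and at completion of each session". Its stops include dyspnea and other symptoms, onset of angina, "excessive blood pressure (systolic BP > 200 mm Hg, diastolic BP >110 mm Hg"), and a "drop in systolic BP >10 mm Hg and inappropriate bradycardia (drop in heart rate >15 bpm").
- **Section E, 2.b Protection Against Risk.** For training sessions it lists symptoms, angina, systolic pressure above 220 or diastolic above 110 mmHg, and a heart-rate drop of more than 10 beats per minute. It gives no blood-pressure fall and no saturation limit.

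Separately, the eligibility text in sections D and E requires every trainee to complete the tolerance test and also to be cleared by the study cardiologist. It excludes several cardiac histories, including "angina or dyspnea at rest or during ADL's".

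**The concern.** Staff apply stopping rules in real time, so a rule has to be readable in one way only and must not be contradicted elsewhere in the protocol. Here the same reading can end an exercise bout under one section and not under another. One criterion can also be applied in two ways by two testers who both follow the text.

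What is at stake is first the consistent protection of all 28 trainees, in the tolerance test and then over 24 sessions. There is also a smaller consequence for the data: which sessions are cut short, and possibly who enters or completes training, could depend on which section a tester had in hand.

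**Working it through.** No sample size, power or error rate is involved, so the check is a comparison of the three texts.

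| Criterion | Tolerance test (D) | Testing and training (D) | Training (E, 2.b) |
|---|---|---|---|
| Pressure ceiling, mmHg | at or above 220/120 | above 200 / above 110 | above 220 / above 110 |
| Pressure fall | diastolic, more than 20 mmHg | systolic, more than 10 mmHg | none listed |
| Heart-rate drop | none listed | more than 15 bpm | more than 10 bpm |
| Saturation | below 85% | none listed | none listed |

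**1. Joint or separate?** In the tolerance test, the diastolic fall and the saturation limit share one number and are joined by *and*. Read as joint, a diastolic fall of 25 mmHg at 95% saturation is not a stop, and neither is 80% saturation without such a fall. Read as separate, each is a stop. The systolic fall and bradycardia in the section D monitoring text are joined by *and* in the same way and have the same ambiguity.

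**2. Ceilings.** Take 210/100 mmHg, assuming that exceeding either limit is enough.
- Section D monitoring: 210 > 200, a stop.
- Tolerance test: 210 < 220 and 100 < 120, not a stop.
- Section E: 210 < 220 and 100 < 110, not a stop.

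If both limits must be exceeded, 210/100 is not a stop anywhere, but the conflict remains. At 210/115 both section D monitoring limits are passed (210 > 200, 115 > 110), neither tolerance-test limit is reached (210 < 220, 115 < 120), and the section E pair is not met (210 < 220).

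**3. Pressure fall.** Take systolic 160 to 130 mmHg (a fall of 30), stable diastolic pressure, normal saturation and a heart-rate drop of more than 15 bpm.
- Section D monitoring: a stop on either reading of *and*, because 30 > 10 and the heart-rate condition is also met.
- Tolerance test: no clinical stop on either reading, because there is no diastolic fall and no desaturation.

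**4. Heart-rate drop.** Take a drop of 12 bpm with nothing else abnormal. It is a stop in section E (12 > 10) and not in section D monitoring (12 < 15). Both texts govern training sessions, so this conflict does not depend on whether the tolerance test counts as testing.

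**5. Scope.** The section D monitoring text covers testing and training, directly follows the tolerance-test text, and neither names nor excludes that test. If it applies there, the test's own ceiling can never operate: any reading at or above 220/120 has already passed 200/110. If it does not apply, the protocol should say so.

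**The case against.** The strongest reply has three parts.

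First, the *and* in the tolerance test is probably loose list punctuation. Low saturation is not a form of hypotension, and the ECG list that follows uses *and* before its last item for plainly separate criteria. That is plausible, and the joint reading should not be called the intended one. What stands is that the text permits both.

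Second, a graded maximal test and a study session are different procedures, so different limits need not be an error. That also stands, as far as it goes. It explains a difference between the tolerance test and the sessions only if the scope is stated, and it does not touch the conflict between sections D and E over training sessions.

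Third, the missing consequence for non-ECG stops may be deliberate, because it leaves the decision to the cardiologist. This is fair. It is a gap in documentation, not a contradiction.

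A reader might go further and infer that a patient with a dangerous response could pass the only cardiac gate. The documents do not support this. Clearance by the study cardiologist is a separate, mandatory condition. Cardiac-history exclusions apply. Angina and dyspnea stop the tolerance test on their own. Section E, 1.c, lists cardiologists among the staff present and available. Silence about non-ECG stops is therefore not an automatic pass.

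A reader might also combine a 30 mmHg systolic fall with 84% saturation and no heart-rate drop, and call this a stop under section D monitoring that the tolerance test misses. That needs *and* to be read loosely in one place and strictly in the other. Read loosely in both, 84% already stops the tolerance test. Read strictly in both, the section D monitoring criterion is not met.

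**Conclusion.** The concern holds as one of contradictory and ambiguous stopping criteria. The conflict between section D monitoring and section E over training sessions is certain: the systolic ceilings differ by 220 − 200 = 20 mmHg and the heart-rate limits by 15 − 10 = 5 bpm. The conflict between the tolerance test and section D monitoring is direct if testing includes the tolerance test; otherwise it is an unstated scope. The joint-or-separate question is an ambiguity of wording.

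The 210/100 example assumes that either pressure limit is enough. The systolic-fall example assumes no symptom or ECG stop at the same time. The rules cover all 28 trainees, but the documents give no figures from which to estimate how often the sections would disagree in practice, or any effect on the results. The undocumented path from a non-ECG stop to clearance is a secondary matter of missing detail. Nothing here shows which limits are right. The change should be made before training starts, because it is cheap and concerns safety rules.

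**What to change.** Reconcile the three texts, with the study cardiologist setting every limit and disposition.

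- State which set of criteria governs the tolerance test and which governs study testing and training sessions. Give one set for training sessions in both section D and section E.
- In the tolerance test, make clear whether the blood-pressure fall and the saturation limit are joint or separate. Do the same for the systolic fall and heart-rate drop in section D monitoring, and for the paired systolic and diastolic ceilings.
- If the tolerance test is meant to differ from the sessions, say so and give the reason.
- State how a tolerance test stopped for a non-ECG reason feeds into the required cardiologist clearance, including whether a test stopped early counts as completed.

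The cost is protocol wording and matching entries on the test and session forms. Design, sample size and analysis are unchanged.
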